# 11.13 Acute Kidney Injury

Incidence rate on the Phase III Study (NO25026) was 10% among patients who received vemurafenib versus 1.4% who received dacarbazine. Approximately 40% patients receiving vemurafenib developed creatinine elevations at some point in the study compared to patients receiving dacarbazine (6%).

# 11.14 Potential for Drug-Drug Interaction

#### 11.14.1 Effects of Vemurafenib on Drug Metabolizing Enzymes

Vemurafenib is a moderate CYP1A2 inhibitor, a weak CYP2D6 inhibitor, and a CYP3A4 inducer. Co-administration of vemurafenib increased the AUC of caffeine (CYP1A2 substrate)

2.6-fold and increased the AUC of dextromethorphan (CYP2D6 substrate) by 47%, while it decreased the AUC of midazolam (CYP3A4 substrate) by 39%. Concomitant use of vemurafenib with agents with narrow therapeutic windows that are metabolized by CYP1A2, CYP2D6 and CYP3A4 is not recommended as vemurafenib may alter their concentrations. If coadministration cannot be avoided, exercise caution and consider a dose reduction of the concomitant CYP1A2 and CYP2D6 substrate drug. Co-administration of vemurafenib resulted in an 18% increase in AUC of S-warfarin (CYP2C9 substrate). Exercise caution and consider additional INR monitoring when vemurafenib is used concomitantly with warfarin.

# 11.14.2 Drugs that Inhibit or Induce CYP3A4

Vemurafenib is a substrate of CYP3A4, and therefore, concomitant administration of strong CYP3A4 inhibitors or inducers may alter vemurafenib concentrations. Strong CYP3A4 inhibitors (e.g. ketoconazole, itraconazole, clarithromycin, atazanavir, nefazodone, saquinavir, telithromycin, ritonavir, indinavir, nelfinavir, voriconazole) and inducers (e.g. phenytoin, carbamazepine, rifampin, rifabutin, rifapentine, phenobarbital) should be used with caution when co-administered with vemurafenib.

Appendix A includes a non-exhaustive list of typical examples of CYP1A2 and CYP2C9 substrates and CYP3A4 inducers and inhibitors.

# 12.0 CRITERIA FOR THERAPEUTIC RESPONSE/OUTCOME ASSESSMENT

Response will be determined by the Consensus Resolution response criteria.

# **Complete Response (CR)**

- A morphological absence of hairy cells in the blood and bone marrow
- A normalization of any organomegaly and cytopenias

# Partial response (PR)

- A normalization of cytopenias
- Circulating hairy cells ≤5% of lymphocytes
- ≥50% reduction in organomegaly and bone marrow hairy cells.

#### All other responses are considered as no response (NR)

# Relapse after CR

- Reappearance of hairy cells in the blood or bone marrow
- Development of cytopenias and/or organomegaly on physical examination

#### Relapse after PR

• >50% increase of residual disease

#### 13.0 CRITERIA FOR REMOVAL FROM STUDY

- Ineligibility (at the pretreatment evaluation) of the patient as defined in the inclusion/exclusion criteria
- Unacceptable toxicity (as defined in Section 11.0)
- Disease progression requiring alternate therapy (will still be followed for survival)
- Significant protocol violation

- Non-compliance of the patient
- Refusal of the patient to continue treatment and/or observation
- Unrelated medical illness or complication that increase the risk of protocol therapy to unacceptable levels
- Decision by the Investigator that termination is in the patient's best medical interest
- Lost to follow-up
- Death of the patient

# 14.0 BIOSTATISTICS

The primary objective of this phase II trial is to determine the overall response rate after therapy with the BRAF inhibitor, Vemurafenib, in patients with relapsed and refractory HCL. The outcome is determined as the overall response by three months. Currently, there is no standard treatment for these patients.

We propose a single arm, multi-center, open-label, phase II study of Vemurafenib in patients with HCL who are resistant to or intolerant of purine analogs, who have relapsed disease within 2 years of purine analog-based therapy, or who have ≥ 2 relapses. A Simon's mini-max two-stage design will be employed to assess the efficacy of Vemurafenib. Without a standard of care for these relapsed or refractory patients, there is no well-estimated historical benchmark to base the response rates for this trial. However, an observed response rate of at least 20% would provide sufficient evidence that vemurafenib should be further investigated in this patient population. Therefore, this study is designed such that a 20% overall response rate (PR or better) by three months would not be considered promising, while a 40% response rate would be considered promising.

In the first stage of the study, 19 patients will be treated. If 3 or fewer responses are seen among the first 19 patients, the study will be closed for lack of efficacy. If at least 4 patients respond to the treatment, then an additional 17 patients will be accrued to the second stage. At the end of the trial, if 11 or more patients have responded out of the 36 patients then the drug will be considered worthy of further investigation. The Type I and Type II errors are both 0.10. Safety and tolerability data of the intervention will be tabulated across all study subjects.

In addition to the primary outcome, there are a number of secondary objectives for this trial. Kaplan-Meier methodology will be used to estimate the time to response, duration of response, and progression-free and overall survival. Throughout the study, MRD will be evaluated to determine whether individuals who achieved CR have residual disease by IHC.

High throughput next generation sequencing will explore the mutation profile for BRAF and 29 additional genes at baseline and after three treatment cycles. These binary data will be descriptively reviewed by treatment response.

Pre- and post-treatment peripheral blood or bone marrow samples will be assessed by Western Blot and/or phospho-flow cytometry for downstream targets of BRAF (MEK, pMEK, ERK, pERK). These binary pre/post data will be tabulated across the sample to describe the pharmacodynamics of the intervention. The data will also be compared to a new assay developed by the [name] lab.

The final secondary objective will explore various biomarkers at baseline to investigate whether any are more frequently observed in individuals who are refractory or resistant to vemurafenib. These biomarkers will additionally be obtained in patients who are refractory to vemurafenib

after three cycles of treatment or in patients who relapse after vemurafenib. The biomarkers are described in Section 10.3.

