# **Secondary Objectives**

- 1. To assess the safety and tolerability of vemurafenib in patients with HCL
- 2. To assess the efficacy of vemurafenib based on time to response, duration of response, and kinetics of minimal residual disease (MRD) response assessed by immunohistochemistry
- 3. To determine the progression-free and overall survival of HCL patients treated with vemurafenib
- 4. To characterize molecular profiling of HCL by high throughput next generation sequencing using Raindance multiplex PCR and Ilumina next generation sequencing
- 5. To assess the pharmacodynamics of vemurafenib via measurement of BRAF downstream targets (MEK, p-MEK, ERK, p-ERK) from the peripheral blood or bone marrow aspirate samples, and by examining the MAPK, PI3K and JAK-STAT signaling pathways using Cell Biosciences NanoPro 1000 technology
- 6. To evaluate biomarkers that may be relevant to explain primary or acquired resistance to vemurafenib as assessed by additional BRAF mutations, reactivation of MAPK pathways, activation of alternative signaling pathways (e.g. PI3K and STAT)

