# 3.6 BRAF Inhibitor, Vemurafenib: Clinical Data in Melanoma

The BRAF inhibitor, vemurafenib (previously known as PLX4032 and RO5185426), has been extensively studied both in preclinical models and in clinical trials. *In vitro* studies have demonstrated that PLX4032 selectively inhibits the growth of tumor cells expressing BRAF V600E mutation by inhibiting ERK signaling only in mutant BRAF tumor cells, thus achieving a broader therapeutic index without causing toxicity resulting from the inhibition of ERK signaling in normal cells. This is in contrast to MAPK/ERK (MEK) inhibitors that inhibit ERK phosphorylation in both normal and tumor cells. The anti-tumor efficacy of PLX4032 was also demonstrated in several *in vivo* studies using tumor xenograft models of BRAF V600E mutant melanoma with partial or complete tumor regressions and improved animal survival with no significant toxicity.

Based on these preclinical data, several clinical trials have been conducted in patients with metastatic melanoma where approximately 50% of patients carry the BRAF V600E mutation. In a phase I trial, the maximum tolerated dose of 960mg twice daily was established, and frequent tumor regressions were observed. Notably, the analysis of paired tumor biopsies (at baseline and at day 15 of PLX4032 treatment) revealed a strong correlation between a decrease in phosphorylated ERK and a clinical response, suggesting that PLX4032 inhibited the MAP kinase pathway (at 960mg twice daily dosing level) and the need to obtain effective ERK signaling inhibition for significant tumor response. In a phase II trial involving patients with previously treated metastatic melanoma harboring the BRAF V600E mutation, a response rate of 53% was observed with a median duration of response of 6.7 months. More recently, the results from a randomized, multicenter phase III trial was published, demonstrating a remarkable activity in patients with BRAF-mutated metastatic melanoma with a response rate of 48% (compared to 5% in patients treated with standard chemotherapy dacarbazine) and a relative reduction of 63% in the risk of death. Common adverse events noted in these trials with vemurafenib in melanoma patients included arthralgia, rash, fatigue, alopecia, keratoacanthoma, photosensitivity, nausea, diarrhea and squamous-cell carcinoma, but with very little hematologic toxicity.

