#### 10.3 Research Tests

The following research tests will be performed at the time points indicated in **Table 1**. Bone marrow aspirate samples will be collected in an EDTA-containing syringe (3-5ml) and peripheral blood samples will be collected in either green top or purple top tubes (10ml). At each specified time point (Table 1), 3 green or purple top tubes of peripheral blood samples will be collected. These samples can be collected locally if the patient has an established local oncologist and only after discussing with the study PI. The collected samples will be delivered to the [name]'s laboratory in [name] at Memorial Sloan-Kettering Cancer Center.

**BRAF Mutation Analysis:** Peripheral blood and/or bone marrow aspirate samples from pretreatment and post-treatment at specified time points will be assessed for BRAF V600E mutation by allele-specific PCR of genomic DNA followed by conventional agarose-gel electrophoresis and/or by quantitative real-time allele-specific PCR in complimentary DNA (cDNA).

Pharmacodynamic (PD) Studies: Peripheral blood and/or bone marrow aspirate samples from pre-treatment and post-treatment at specified time points will be assessed by Western Blot or by phospho-flow for the downstream targets of BRAF (MEK, pMEK, ERK, pERK) to assess the on-target effect of the Vemurafenib. In addition, signaling studies using Cell Biosciences NanoPro 1000 technology will be performed on the same samples, which will allow us to obtain accurate, quantitative signaling on the entire MAPK, PI3K, and JAK-STAT pathways before and after treatment on sorted circulating hairy cells.

\*For MSKCC Patients ONLY: Additional research blood samples for the above mentioned pharmacodynamic studies will be collected in patients who receive their treatment at MSKCC. These additional time points include 2-4 hours and 24 hours after the first dose of vemurafenib. 24-hour blood sample can be collected locally if the patient has an established local oncologist and only after discussing with the MSKCC PI.

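### Section 14 reports the pharmacodynamic objective as a binary table with no cut-off and states no analysis for the quantitative NanoPro data, so the size of pathway suppression would go unreported

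*Combined protocol and SAP*

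**What the plan says.** Secondary objective 5 (Section 2.0) is "To assess the pharmacodynamics of vemurafenib via measurement of BRAF downstream targets", together with MAPK, PI3K and JAK-STAT signalling by the NanoPro 1000 platform.

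Section 10.3 describes two sets of measurements on blood and/or marrow taken before and after treatment. The first is Western blot or phospho-flow for MEK, pMEK, ERK and pERK. The second is NanoPro: "signaling studies using Cell Biosciences NanoPro 1000 technology will be performed on the same samples", which is expected to give "accurate, quantitative signaling on the entire MAPK, PI3K, and JAK-STAT pathways before and after treatment", on sorted circulating hairy cells. Table 1 schedules research blood at screening, repeatedly in cycle 1, and at later visits. The lead centre adds samples 2-4 hours and 24 hours after the first dose.

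Section 14.0 deals with this objective in one short paragraph. It names Western blot and/or phospho-flow and the four targets, then says: "These binary pre/post data will be tabulated across the sample to describe the pharmacodynamics of the intervention". It adds only that "The data will also be compared to a new assay developed by the" (laboratory name removed) and gives no method for that comparison. NanoPro is not mentioned there.

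**The concern.** A binary table shows how many patients fell on each side of a line. It does not show how far signalling fell, when it fell, or how much patients differed. Here the line itself is undefined, so the table could change with a threshold chosen after the data are seen. The measurements that the protocol itself calls quantitative have no stated analysis at all.

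This matters because pERK suppression supports the protocol's reasoning. Section 3.6 cites, in melanoma, a "strong correlation between a decrease in phosphorylated ERK and a clinical response", and Section 3.8 uses pERK suppression to support the dose. Section 14.0 reviews the sequencing data by treatment response but plans no such display for the pharmacodynamic data. With at most 36 patients and accrual closed (Section 1.0), analysis is the only remaining way to get more from these samples.

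**Working it through.** **1. The plan's own figure.** The only design figure in Section 14.0 belongs to the primary endpoint: stop if 3 or fewer of 19 respond; success if 11 or more of 36 respond; null rate 0.20, target rate 0.40, both errors 0.10. The probability of success at response rate p is the sum over x = 4 to 19 of P(X = x) × P(Y ≥ 11 − x), with X binomial(19, p) and Y binomial(17, p). At p = 0.20 this is 0.086; at p = 0.40 it is 0.902. A search for the smallest total size meeting both limits returns the same design. The primary design reproduces and is not in question. No figure is stated for the pharmacodynamic objective.

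**2. Assay against analysis.**

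| Readout | Scale stated in Section 10.3 | Analysis in Section 14.0 |
|---|---|---|
| MEK, pMEK, ERK, pERK by blot or phospho-flow | none stated | binary table, no cut-off |
| MAPK, PI3K, JAK-STAT by NanoPro | quantitative | none stated |

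Neither row yields a size of change.

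**3. Information lost by a binary call.** The documents give no standard deviation, effect size or cut-off for these readouts, so I assume a normal readout and vary the cut. For small shifts, a value cut at c, with a proportion p on one side, keeps φ(c)² / [p(1 − p)] of the information in the continuous value, φ being the standard normal density. At a median cut this is 0.3989² / 0.25 = 0.637 (= 2/π), and 36 × 0.637 = 22.9.

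| Split at the cut | Information kept | Lost | 36 patients act like |
|---|---|---|---|
| 50/50 | 0.637 | 36% | 22.9 |
| 30/70 | 0.576 | 42% | 20.7 |
| 20/80 | 0.490 | 51% | 17.6 |
| 10/90 | 0.342 | 66% | 12.3 |
| 5/95 | 0.224 | 78% | 8.1 |

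The median split is the best case. These figures treat each readout on its own. Positive pre/post correlation makes the loss larger for a paired comparison. With correlation 0.5 and a median cut, the binary values correlate (2/π) × arcsin(0.5) = 1/3, and the share kept is 0.637 × (1 − 0.5)/(1 − 1/3) = 0.48.

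**4. Dependence on effect size.** Simulated pairs, all inputs assumed: normal, correlation 0.5, cut at the pre-treatment median, two-sided 5%, paired t-test on the values against exact McNemar on the binary calls.

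| Shift (SD) | 36 pairs: continuous / binary | 20 pairs: continuous / binary |
|---|---|---|
| 0.5 | 0.83 / 0.39 | 0.56 / 0.17 |
| 1.0 | 1.00 / 0.93 | 0.99 / 0.62 |
| 1.5 | 1.00 / 1.00 | 1.00 / 0.89 |

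The binary figure also moves with the test and the cut. At 36 pairs and 0.5 SD, mid-p McNemar gives 0.50 with the cut midway between the pre and post means, and 0.38 with the cut 1 SD below the pre mean. At 0.8 SD the same two cuts give 0.88 and 0.82, against about 1.00 for the continuous values.

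**The case against.** The strongest reply is that this is a descriptive laboratory objective with no hypothesis. No pharmacodynamic test exists to lose power, every input to the power figures is assumed, and nothing in Section 14.0 forbids reporting graded values. Section 3.5 also expects a large effect: marked inhibition at 1 μM or less, with about 80 μM achievable. At a 1.5 SD shift with 36 pairs the gap vanishes. All of this stands. It limits the power figures to illustration and caps the importance of the point. It does not supply a cut-off, or an analysis for the NanoPro data.

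Four stronger readings are tempting, and the documents do not support them:

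- That the NanoPro values will be dichotomised. Section 14.0 attaches the binary description to blot and phospho-flow; for NanoPro it is silent.
- That the protocol calls phospho-flow quantitative. Section 10.3 uses that word only for NanoPro.
- That Section 3.6 says the size of the pERK fall tracks response. It reports a correlation with a decrease. Depth of suppression is a natural next question, but the protocol does not state it as a finding.
- That pairing is ignored. A pre/post table can be laid out as pairs; the plan does not say whether it will be.

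A practical objection also stands. Assay and tissue may differ between patients or visits, and ratios across them are not comparable. NanoPro uses sorted circulating hairy cells, while complete response under Section 12.0 requires their absence from blood. The best responders may therefore have no post-treatment value. The fix has to handle both.

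**Conclusion.** The point holds as a cheap improvement to a secondary objective. The stated method is a binary table without a cut-off, the quantitative data have no stated analysis, and the plan as written would report no size of pathway suppression. If a readout is roughly normal, the binary call discards at least about 36% of the information (36 patients act like about 23 or fewer), and 51% to 78% if the cut leaves 20% to 5% of values on one side. These percentages rest on the normal assumption, small shifts and a pre/post correlation that is not negative. If nearly every patient shows near-complete suppression, the practical loss is small.

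A reader might infer that the trial is underpowered or its conclusion at risk. It is not: the primary endpoint, its two-stage rule and its error rates do not depend on this analysis.

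**What to change.** In Section 14.0:

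- For phospho-flow and NanoPro values measured on a continuous scale, report the within-patient log ratio (post/pre) at each scheduled time point as a median with 95% confidence interval. Form ratios only within the same assay and tissue. Show them descriptively by response.
- State how values below an assay's detection limit enter the ratio, because the log ratio is undefined at zero.
- Keep the binary table for blots read as present or absent, with the cut-off stated and a paired pre-by-post layout.
- Give the number of usable pairs at each time point. Count and report missing post-treatment values, separately for complete responders without circulating hairy cells.
- Say how the comparison with the new assay will be made.
- If the data have already been examined, label the analysis post hoc.

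The cost is a few lines of text and slightly more analysis, with no new samples, assays or visits. The price is fewer usable pairs where assay or tissue differs, and a display by response that must be read with the missing values in view.

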#### 15.0 RESEARCH PARTICIPANT REGISTRATION AND RANDOMIZATION PROCEDURES

# 15.1 Research Participant Registration

Confirm eligibility as defined in the section entitled Inclusion/Exclusion Criteria. Obtain informed consent, by following procedures defined in section entitled Informed Consent Procedures. During the registration process registering individuals will be required to complete a protocol specific Eligibility Checklist. The individual signing the Eligibility Checklist is confirming whether the participant is eligible to enroll in the study. Study staff are responsible for ensuring that all institutional requirements necessary to enroll a participant to the study have been completed. See related Clinical Research Policy and Procedure #401 (Protocol Participant Registration).

All participants must be registered through CTMS.

#### 15.2 Randomization

There is no randomization in this trial.

#### 16.0 DATA MANAGEMENT ISSUES

This is a multicenter trial that will be coordinated by the Multicenter Core group at MSKCC. A Clinical Research Associate (CRA) will be assigned to the study. The responsibilities of the CRA include project compliance, data collection, abstraction and entry, data reporting, regulatory monitoring, problem resolution and prioritization, and coordinate the activities of the protocol study team. The data collected for this study will be entered into a secure database. Source documentation will be available to support the computerized patient record.

# 16.1 Quality Assurance

Weekly registration reports will be generated to monitor patient accruals and completeness of registration data. Routine data quality reports will be generated to assess missing data and inconsistencies. Accrual rates and extent and accuracy of evaluation and follow-up will be monitored periodically throughout the study period and potential problems will be brought to the attention of the study team for discussion and action. Random-sample data quality and protocol compliance audits will be conducted by the study team, at a minimum of two times per year, more frequently if indicated. Additionally, monthly teleconferences including principal investigators and/or their designees from all sites will be held to expedite the review of toxicity and efficacy data.

# 16.2 Data and Safety Monitoring

The Data and Safety Monitoring (DSM) Plans at Memorial Sloan-Kettering Cancer Center were approved by the National Cancer Institute in August 2018. The plans address the new policies set forth by the NCI in the document entitled ""Policy of the National Cancer Institute for Data and Safety Monitoring of Clinical Trials."

Memorial Sloan Kettering Cancer Center IRB Number: 12-200 A(17)

Approval date: 15-Jun-2022

There are several different mechanisms by which clinical trials are monitored for data, safety and quality. At a departmental/PI level there exists procedures for quality control by the research team(s). Institutional processes in place for quality assurance include protocol monitoring, compliance and data verification audits, staff education on clinical research QA and two institutional committees that are responsible for monitoring the activities of our clinical trials programs. The committees: Data and Safety Monitoring Committee (DSMC) for Phase I and II clinical trials, and the Data and Safety Monitoring Board (DSMB) for Phase III clinical trials, report to the Deputy Physician-in-Chief, Clinical Research.

The degree of monitoring required will be determined based on level of risk and documented.

The MSK DSMB monitors phase III trials and the DSMC monitors non-phase III trials. The DSMB/C have oversight over the following trials:

- MSK Investigator Initiated Trials (IITs; MSK as sponsor)
- External studies where MSK is the data coordinating center
- Low risk studies identified as requiring DSMB/C review

The DSMC will initiate review following the enrollment of the first participant/or by the end of the year one if no accruals and will continue for the study lifecycle until there are no participants under active therapy and the protocol has closed to accrual. The DSMB will initiate review once the protocol is open to accrual.

